## 2.2. Analysis Populations

The primary efficacy analysis population will be the Full Analysis Set (FAS) population, defined as all randomized patients in the high-risk proteinuria group. Patients will be grouped by their assigned treatment. When considering the all-patients population (baseline 24-hour UPE  $> 1$  g/day), the same principal applies, i.e. the FAS for this population is defined as all randomized patients.

The supporting efficacy analysis populations will be the Per-Protocol Analysis Set population, which includes all randomized high-risk proteinuria patients who receive at least 10 doses of study drug in the Initial Treatment Period and have non-missing primary endpoint data (24-hour UPE at baseline and Week 36). Patients will be grouped by their assigned treatment.

Safety analyses will be based on the Safety Analysis Set, which includes all patients who receive any positive amount of study drug. Patients will be grouped by their actual treatment received. Supportive safety summaries will also be made in the population of all patients who receive any positive amount of study drug.

## 2.3. Estimand Framework for the Primary and Key Secondary Endpoints

Care is needed when selecting an estimand since the ICH E9 Estimand Addendum unfortunately promotes analyses that do not respect the randomization, such as ‘theoretical’ and ‘while on

treatment' estimands, and, thus, are likely to be heavily biased. The principal estimands chosen for the primary and key secondary efficacy endpoints outlined in [Table 1](#) avoid such bias by respecting the randomization.

**Table 1: Estimands For The Primary and Key Secondary Efficacy Endpoints**

Endpoint	Treatment Policy Estimands
Primary	
Primary UPE Endpoint, Patients With Baseline UPE $\geq 2$ g/day	
 
• Treatment regimens to be evaluated = narsoplimab and placebo
 
• The patient population to be evaluated = FAS of all randomized patients with a baseline UPE <math>\geq 2</math> g/day.
 
• The primary UPE endpoint will be analyzed and formally tested for treatment comparison with first 180 patients in the high-risk proteinuria group through 36 weeks in the FAS population.
 
• Patient-level outcome to be analyzed = log change in UPE from baseline to weeks 12, 24, 30 and 36 post randomization, analyzed via mixed model repeated measures analysis (MMRM).
 
• Intercurrent events handling = all patients will be followed for UPE endpoint attainment regardless of early cessation of randomized treatment or the occurrence of intercurrent events such as the use additional systemic therapies.
 
• The population-level estimate of treatment effect = the difference between narsoplimab and placebo in LSmean UPE log change from baseline to 9 months as extracted from the MMRM analysis.
 

**Table 1: Estimands For The Primary and Key Secondary Efficacy Endpoints (Continued)**

Endpoint	Treatment Policy Estimands
Key Secondary eGFR Endpoint, Patients With Baseline UPE $\geq 2$ g/day	
 
• Treatment regimens to be evaluated = As Primary UPE Endpoint.
 
• The patient population to be evaluated = As Primary UPE Endpoint.
 
• Patient-level outcome to be analyzed = eGFR values collected at 12, 24, 36, 48, 60, 72, 84 and 96 weeks post randomization, analyzed via mixed model repeated measures random coefficients analysis.
 
• Intercurrent events handling = Intercurrent events handling = As Primary UPE Endpoint.
 
• The population-level estimate of treatment effect = the difference between narsoplimab and placebo in eGFR total slope over 96 weeks.
 

Key Secondary eGFR Endpoint, Patients With Baseline UPE $> 1$ g/day	
 
• Treatment regimens to be evaluated = As Primary UPE Endpoint
 
• The patient population to be evaluated = FAS of all randomized patients with a baseline UPE <math>> 1</math> g/day.
 
• Patient-level outcome to be analyzed = eGFR values collected at 12, 24, 36, 48, 60, 72, 84, and 96 weeks post randomization, analyzed via mixed model repeated measures random coefficients analysis.
 
• Intercurrent events handling = As Primary UPE Endpoint.
 
• The population-level estimate of treatment effect = the difference between narsoplimab and placebo in eGFR total slope over 96 weeks.
 

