### 1.3.2. Sample Size for Key Secondary Rate of Change in eGFR Endpoints

Data from IgAN database from the University of Leicester, UK, provides the basis for the power calculation for eGFR Rate of Decline over 2 years in patients with a baseline UPE  $\geq$  2 g/day. Patients on ACE/ARBs with a baseline UPCR of  $\geq$  2 g/day were identified and their eGFR values over 3 to 24 months were assigned to 3 monthly windows to reflect the intended sampling schedule in the OMS721-IGA-001 protocol.

A random coefficients model was applied using SAS PROC MIXED. The form of the model was:

$$yyyy_{iijj} = (\beta_0\beta_0 + bbb_0) + (\beta_2\beta_2 + bbb_2)xxxx_{iijj} + eeee_{iijj}$$

where

- $yyyy_{iijj}$  is the eGFR value for patient  $iijj$  at assessment time  $jjjj$ ;

- $xxxx_{iiiiii}$  is the time of the  $jjjjttth$  assessment for patient  $iiii$ ;
- $\beta\beta\beta\beta_0$  and  $\beta\beta\beta\beta_2$  are the overall fixed effects of intercept and time (or slope);
- $bbbb_{0iiii}$  and  $bbbb_{2iiii}$  are the random intercept and slope effect associated with patient  $iiii$ ;
- $eeee_{iiiiii}$  are the residual error for patient  $iiii$  at time  $jjjj$ ;

The random effects,  $bbbb_{0iiii}$  and  $bbbb_{2iiii}$  are assumed  $iiii. iii. dddd$  Normally distributed with variance components  $\sigma\sigma\sigma_0^2$  and  $\sigma\sigma\sigma_2^2$  and, independently, the random error  $eeee_{iiiiii}$  is Normally distributed with variance  $\sigma\sigma_{ee\varphi_e}^2$ .

The annualized eGFR rate of decline was thus estimated to be  $-5.44$  mL/min/m $^2$  (SE 0.1869 mL/min/m $^2$ ), the between slope variance component  $\sigma\sigma\sigma_2^2$  was estimated to be 6.4932 $^2$  mL/min/m $^2$  annually ( $= 0.7356^2$  mL/min/m $^2$  monthly), and the residual error variance  $\sigma\sigma_{ee\varphi_e}^2$  was estimated to be  $= 6.5077^2$  mL/min/m $^2$ .

The hypothesis for the rate of change in eGFR over 24 months in patients with a baseline UPE  $\geq 2$  g/day is,

$$H_0: \beta\beta\beta\beta_d = \beta\beta\beta\beta_p$$

$$H_1: \beta\beta\beta\beta_d \neq \beta\beta\beta\beta_p$$

where  $\beta\beta\beta\beta_d$  and  $\beta\beta\beta\beta_p$  represent the annualized slope for eGFR over 24 months for narsoplimab and placebo, respectively. As per [Zhao 2021] and [Carroll 2023] (submitted), the required sample size is given by,

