$$n = \frac{4(zzzz_{aaaa} + zzzz_{pppp})^2}{(\beta\beta\beta\beta_{DDDD} - \beta\beta\beta\beta_{PPPP})^2} \cdot \frac{\sigma\sigma\sigma_{eeee}^2 + \sigma\sigma\sigma_{bb}^2}{SSSS_{xxxxxxxxxx}}$$

where  $\alpha$  is the 1-sided Type I error,  $\beta$  Type II error,  $zzzz_{aaaa} = \Phi^{-1}(1 - \alpha)$  where  $\Phi^{-1}(\cdot)$  represents the inverse standard Normal distribution function, and  $SSSS_{xxxxxxxxxx}$  is the sum of the squared differences of eGFR measurement times minus the mean time. With eGFR measured 3 monthly over 24 months, then  $SSSS_{xxxxxxxxxx} = 378$ .

Thus, hypothesizing that the 2-year annualized eGFR rate of decline for narsoplimab relative to placebo in the high-risk proteinuria group (baseline UPE  $\geq 2$  g/day) is 3.48 mL/min/1.73 m $^2$ , a sample size of 280 patients (i.e., 140 per treatment group) followed for 2 years post randomization will provide at least 85% power at the 2-sided 5% level to test this hypothesis. Further, the smallest observed improvement in the UPE  $\geq 2$  g/day population that will yield  $p \leq 0.025$  1-sided with  $N = 280$  is 2.3 mL/min/year, in line with [Inker 2021].

Similarly, data from the University of Leicester registry provide an estimate of the annualized eGFR rate of decline in patients with a baseline UPCR of  $> 1$  g/day of  $-4.40$  mL/min/m $^2$  (SE 1.716 mL/min/m $^2$ ), and the between-slope variance component  $\sigma\sigma\sigma_2^2$  was estimated to be 7.8469 $^2$  mL/min/m $^2$  annually ( $= 0.6539^2$  mL/min/m $^2$  monthly) with the residual-error variance  $\sigma\sigma_{ee\varphi_e}^2$  estimated to be  $= 5.9517^2$  mL/min/m $^2$ .

Hypothesizing that the 2-year annualized eGFR rate of decline for narsoplimab relative to placebo in the all-patients population is 2.45 mL/min/1.73 m $^2$ , a sample size of 450 patients

(i.e., 225 per treatment group) followed for 2 years post randomization will provide at least 85% power at the 2-sided 5% level to test this hypothesis. And again, the smallest observed improvement in the overall population that will yield  $p \leq 0.025$  1-sided with  $N = 450$  is 1.6 mL/min/year.

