## 2.7. Analysis Visits

Two sets of analysis visits will be used. The first set ([Table 2](#)) is derived from the regular scheduled visits regardless of additional treatments (extended treatment, relapse retreatment, re-initiation of treatment open-label treatment, and open-label relapse retreatment; see the schedule of events in the protocol). Longitudinal data analyses will be based on the regular scheduled visits and time will be calculated from Day 1, unless otherwise specified.

The second set is derived for the additional treatment scheduled visits ([Table 3](#)).

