**Table 2: Analysis Visits for Regular Scheduled Visits (Continued)**

Visit	Target Day [Week]	Visit Window (Days)
Week 48	330 [48]	289 to 414 [41 to 60wk]
Week 72	498 [72]	415 to 582
Week 96	666 [96]	583 to 750
Week 120	834 [120]	751 to 918
Week 144	1002 [144]	919 to 1086

If there are 2 or more assessments in the same analysis visit, the closest one to the target day will be used in the analysis. If there are 2 assessments that are equally spaced from the target day, the latest one will be used in the analysis, unless otherwise specified.

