### 2.9.2. Efficacy Analyses

Unless otherwise specified, time will be calculated from Day 1.

**Table 2** will be used to determine the analysis values and the timepoints to be used in the analysis regardless of missed visits, extended treatment, or re-initiation of treatment.

The UPE primary efficacy endpoint in the high-risk proteinuria group is unaffected by the associated blinded SSRE and, hence, no special considerations apply to the analysis of UPE data pre and post the planned SSRE.

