$$SSSSxxxxxx_{iiii} = \sum_{iiii=1}^{vvvv} (xxxx_{iiii} - \bar{xxxx})^2 = (mmmm - \bar{mmmm})^2 + (2mmmm - \bar{mmmm})^2 + \dots + (vvvvmmmm - \bar{mmmm})^2 = \frac{mmmm^2 vvvv(vvvv^2 - 1)}{12}$$

Thus,  $VVVV\beta\beta\beta\beta\beta\beta$  can be written as,

$$VVVV\beta\beta\beta\beta\beta\beta = 1 \cdot \sum_{iiii=1}^{vvvv} \frac{\sigma\sigma\sigma^2 ee^2}{SSSSxxxxxx_{iiii}} + \sigma\sigma\sigma^2 \bar{ee}^2 = \frac{2}{NNNN} \cdot \frac{\sigma\sigma\sigma^2}{SSSSxxxxxx_{iiii}} \pm \sigma\sigma\sigma^2 \bar{ee}^2 = \frac{2}{NNNN} \cdot \frac{\sigma\sigma\sigma^2}{\frac{mmmm^2 vvvv(vvvv^2 - 1)}{12}} + \sigma\sigma\sigma^2 \bar{ee}^2$$

Applying the same steps to drug treated patients, Fishers Information,  $IIIFFFF$ , expected at the end of the trial with  $NNNN$  patients followed for  $FFFF$  months is given by

where  $VVVV\beta\beta\beta\beta\alpha_{DD}$  and  $VVVV\beta\beta\beta\beta\alpha_{PP}$  are the variances of the estimated slope values for the drug and placebo groups, respectively.

Fisher's Information for the first N=180 patients, randomized over 45 months and followed for minimum follow-up of 9 months, is easily estimated in SAS to be  $III_{III} = 52.591$  such that the information fraction for eGFR slope would be  $52.591/107.175 = 49.1\%$ ; the associated SAS code for this computation is provided in [Appendix 3](#).

At the time of the primary endpoint analysis with  $N =$  the first 180 high-risk proteinuria patients, the available eGFR data will be analyzed via random coefficients modelling (Section 2.9.2.3) to provide an estimate of the difference in annualized eGFR rate of decline between narsoplimab and placebo,  $\beta_3 - \beta_4$ , along with its standard error,  $\text{SE}(\beta_3 - \beta_4)$ , as well as between slope and residual error variance component estimates,  $\text{SE}(\sigma_s^2)$  and  $\text{SE}(\sigma_e^2)$ . No p-value for the difference in annualized eGFR rate of decline will be generated. Denote the z-value for annualized eGFR rate of decline at the time of the primary endpoint analysis as,

$$zzzz_{\text{iii}} = \frac{\beta}{ssssss(\beta_3)_{\text{iii}}}$$

The CP of confirming a treatment effect on annualized eGFR rate of decline with the planned N = 280 randomized high-risk proteinuria patients followed for 24 months is calculated according to Mehta and Pocock (2011) as,

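### The eGFR slope plan counts values at Weeks 24, 60 and 84 that the protocol does not draw, and whether power reaches 85% turns on an unstated choice about baseline

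*SAP*

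**What the plan says.** **Timepoints.** SAP 2.3, Table 1 sets the patient-level outcome for the high-risk key secondary endpoint as "eGFR values collected at 12, 24, 36, 48, 60, 72, 84 and 96 weeks post randomization", and lists the same weeks for the all-patients endpoint. Appendix 1 uses the same eight weeks for the eGFR imputation, with baseline eGFR as a separate variable.

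**Sizing.** SAP 1.3.2 takes its variance components from a registry in which "eGFR values over 3 to 24 months were assigned to 3 monthly windows to reflect the intended sampling schedule in the OMS721-IGA-001 protocol". It continues: "With eGFR measured 3 monthly over 24 months, then" Sxx = 378. From this, 280 high-risk patients (difference 3.48 mL/min/1.73 m² per year) and 450 patients overall (difference 2.45) each "will provide at least 85% power at the 2-sided 5% level to test this hypothesis". Protocol 14.1.2 repeats the 3-monthly statement and both power claims.

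**Re-estimation.** Appendix 3 uses a 3-month visit interval. SAP 2.9.7 reports interim information 52.591 and final information 107.175, "such that the information fraction for eGFR slope would be" 49.1%. The N* relation in the same section reuses Sxx = 378.

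**Visit rules.** SAP 2.7: "Longitudinal data analyses will be based on the regular scheduled visits". SAP 2.9.2 says that Table 2 "will be used to determine the analysis values and the timepoints to be used in the analysis regardless of missed visits". When a window holds several assessments, "the closest one to the target day will be used in the analysis". SAP Table 2 has no Week 60 or Week 84 visit.

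**What is drawn.** eGFR is reported with the metabolic panel (Protocol 10.1.9, Table 2). Protocol 10.2 and 20.2 schedule that panel at Screening, the final Run-In visit and Weeks 4, 8, 12, 36, 48, 72 and 96. Week 24 is a telephone call plus a 24-hour urine. Weeks 60 and 84 are telephone calls only.

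**The concern.** Three of the eight eGFR values in the estimand have no scheduled blood draw behind them, although the SAP says its 3-monthly grid mirrors the protocol. The SAP is also at odds with itself, since its own visit table lacks two of those weeks.

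Two things follow. First, every quantity built on the grid describes a different schedule from the one being run: Sxx, both power statements, the Appendix 3 information, the 49.1% fraction and the N* relation. Eight values give almost exactly 85%, so there is no margin to absorb the loss of three. Second, the jump-to-placebo and tipping-point analyses for eGFR would impute Weeks 24, 60 and 84 with no scheduled observations to build a model from. Some panels fall outside the regular visits (6RT6, 12RT12, OLT12), but only patients who relapsed or qualified for open-label drug have them, so they cannot stand in for the missing weeks.

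**Working it through.** **Inputs** (SAP 1.3.2 and Appendix 3, monthly units)
- High-risk: residual variance 6.5077² = 42.3499; slope variance 0.7356² = 0.5411; difference 3.48/12 = 0.29; N = 280.
- All patients: residual variance 5.9517² = 35.4227; slope variance 0.6539² = 0.4276; difference 2.45/12 = 0.2042; N = 450.
- Time on the SAP's own scale: 12 weeks = 3 months. No dropout, as in the SAP.

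For the high-risk group the SAP also prints an annual slope component of 6.4932². That does not convert to 0.7356 monthly (0.7356 × 12 = 8.83). The monthly value is the one that reproduces the SAP's results, so it is used here.

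**Formulas**
- V = σe²/Sxx + σb²
- SE = √(4V/N)
- Power = Φ(d/SE − 1.96)
- Information = 1/SE²
- N* = 4 × V × target information

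**Step 1: reproduce the SAP.** Months 3, 6, …, 24 give Sxx = 378.
- High-risk: V = 42.3499/378 + 0.5411 = 0.6531; SE = √(4 × 0.6531/280) = 0.0966; d/SE = 3.002; power = Φ(1.042) = 85.1%; information 107.175, as stated.
- All patients: power 85.1%.

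**Step 2: Table 1's list, drawn weeks only.** Months 3, 9, 12, 18, 24 have mean 13.2, so Sxx = 104.04 + 17.64 + 1.44 + 23.04 + 116.64 = 262.8.
- High-risk: V = 42.3499/262.8 + 0.5411 = 0.7022; SE = 0.1002; d/SE = 2.895; power = Φ(0.935) = 82.5%; information 99.7.
- All patients: V = 35.4227/262.8 + 0.4276 = 0.5624; SE = 0.0707; power 82.3%.
- N for 85% power: about 300 and 485.

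**Step 3: add baseline at time 0.** Months 0, 3, 9, 12, 18, 24 have mean 11, so Sxx = 121 + 64 + 4 + 1 + 49 + 169 = 408. Power is 85.6% and 85.5%; high-risk information is 108.5.

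**Step 4: Weeks 4 and 8.** The Initial Treatment Visit 12 window in SAP Table 2 runs from day 5 to day 120 with target day 78. The one-value rule therefore keeps Week 12 and drops Weeks 4 and 8. They enter only if that rule is overridden.

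| Values in slope model | Sxx | Power, N=280 | Power, N=450 | Final information (high-risk) |
|---|---|---|---|---|
| SAP grid (8) | 378 | 85.1% | 85.1% | 107.2 |
| Weeks 12, 36, 48, 72, 96 | 262.8 | 82.5% | 82.3% | 99.7 |
| + baseline | 408 | 85.6% | 85.5% | 108.5 |
| + Weeks 4, 8, no baseline | 458.9 | 86.2% | 86.2% | 110.5 |
| + baseline, Weeks 4, 8 | 543.9 | 87.0% | 87.0% | 113.1 |

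**Step 5: information fraction.** Numerical integration of the Appendix 3 design (180 patients, 45-month accrual, accrual parameter 2, follow-up 9 to 24 months) gives:
- SAP grid: 52.8/107.2 = 49.3% (SAP, by simulation, 49.1%).
- Five values: 46.9/99.7 = about 47%.
- Five values plus baseline: 56.8/108.5 = about 52%.

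**Step 6: N\* relation, at the planning variances.** For a fixed target, N* scales with V.
- Five values: 0.7022/0.6531 = 1.075. Where the SAP relation returns 280, 301 are needed; above 360/1.075 = 335 the 360 cap is passed.
- With baseline: 0.6449/0.6531 = 0.987, so 280 becomes about 276 and the relation asks for slightly too many.

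**The case against.** The strongest counter-argument is that the SAP's visit rules do not exclude baseline. Table 2 lists the final Run-In visit as a regular analysis visit, and a panel is drawn there. The endpoint is a rate of change from baseline. The slope model in SAP 2.9.2.3 has a random intercept and a treatment contrast on the intercept, but no baseline-eGFR covariate, so a baseline value that is not a time-0 response has no role in it. The same section speaks of limited eGFR data in the first 12 weeks, which suggests that early values were in view. It also measures time by actual assessment day from randomization, though that fixes the time scale and not which values enter.

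This stands in part. A reader might infer that power has been shown to be about 82%. The documents do not support that as a fact: it follows only if baseline stays out, as it does in Table 1, Appendix 1 and Sxx = 378. With baseline in, the claim of at least 85% survives and the N* error changes sign.

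A reader might also infer a threat to Type I error. There is none: the combination weights are fixed at 180/280 and 100/280 and do not use Sxx. Nor is the 85% conditional-power trigger shown to be miscalibrated. That would need observed interim information to be paired with the planned final figure of 107.175, which the SAP does not prescribe.

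The objection does not rescue the three undrawn weeks or the figures built on them.

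**Conclusion.** The mismatch is certain. Sxx = 378, the 49.1% information fraction and the N* relation are computed on a schedule the trial does not have, and the eGFR imputation lists three weeks without scheduled data.

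The effect on power is conditional. Under Table 2's one-value-per-window rule, the 85% claim holds only if baseline enters the slope model: 82.5% and 82.3% without it, 85.6% and 85.5% with it. Overriding that rule to keep Weeks 4 and 8 gives 86% to 87%. The SAP states none of these choices.

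The consequences are moderate: at worst under 3 points of power, an information fraction of about 47% instead of 49.1%, and N* raised by 7.5%. N* stays bounded to 280–360, and the slope and variance components are re-estimated at the interim.

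All figures rest on the SAP's planning variances, no dropout and 12 weeks counted as 3 months. In calendar months (96 weeks = 22.1 months) high-risk power is lower throughout: about 84% on the SAP's eight values, 81.0% on five, and 84.7% on five plus a baseline taken one week before randomization. The ordering is the same, but baseline then no longer lifts power to 85%.

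**What to change.** 1. Remove Weeks 24, 60 and 84 from SAP Table 1 (both endpoints) and from the eGFR list in Appendix 1.
2. In SAP 2.9.2.3, state which scheduled eGFR values enter the slope model, and say explicitly whether baseline is a time-0 response. If Weeks 4 and 8 are to enter, write this as an exception to the Table 2 rule and note that any acute eGFR effect would then feed into the slope.
3. Do this before the interim, when the study is unblinded at study level. A later choice would look data-driven.
4. Recompute Sxx, power, Appendix 3, the information fraction and the N* relation on the stated schedule.
5. Restate power in SAP 1.3.2 and Protocol 14.1.2: about 82% on five post-randomization values, or about 85.5% with baseline.

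The cost is SAP wording, a re-run of Appendix 3 and a matching correction to the protocol text. No new visits are needed. If baseline stays out and power is simply restated, no new patients are needed either. Holding 85% on five values would take about 300 high-risk patients, which is inside the permitted 280–360, and about 485 overall.

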7.2.2. Key Secondary Endpoints

The key secondary endpoints of this study are:

- The rate of change in eGFR up to 96 weeks from baseline in patients with high baseline proteinuria (high-risk proteinuria group; 24-hour UPE \geq 2 g/day)
- The rate of change in eGFR up to 96 weeks from baseline in the all-patients population (24-hour UPE $>$ 1 g/day)

CONFIDENTIAL

No use, disclosure, or reproduction outside of Omertos without prior written authorization

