¹⁵ Vital signs: to be collected prior to dosing, approximately 5 minutes after the end of the 30-minute study drug infusion, and 30 minutes (\pm 5 minutes) following the end of the study drug infusion on study drug treatment days. During the COVID-19 pandemic: For study visits conducted virtually, it may be necessary for patient to collect his or her own pulse, systolic and diastolic BP, and body temperature. Patients will record pulse, systolic and diastolic BP and temperature on a patient diary and provide this diary to the study site. In the case of a thermometer shortage due to the COVID-19 pandemic, sites may allow a patient to collect body temperature with the patient's own thermometer.

¹⁶ During the Run-In visits, these assessments will only be performed if the patient is on stable BP medication and the visit is considered the final Run-In visit

¹⁷ During the Initial Treatment Period ECGs will be collected: pre-dose and at the end of the 30-minute infusion at T1 (to be obtained immediately before the 15-minute post-dose PK/PD samples), and pre-dose at T12

¹⁸ Patients should be instructed to return the 24-hour urine sample to the clinic as soon as possible following its collection. With patient consent, the 24-hour urine collection samples may be delivered from the patient's location to the study site or the central lab by a specialty courier selected by the sponsor.

¹⁹ Due to COVID-19 restrictions, it may be allowable for a local commercial laboratory to assess 24-hour UPE, uPCR, and uACR if neither the study site nor the local commercial lab is able to process and prepare the samples for delivery to the central lab. In this case only, the local commercial lab may assess 24-hour UPE, uPCR and uACR.

²⁰ To be done either before, during, or after T11

²¹ During the COVID-19 pandemic, it may be allowable for CMP, CBC+diff, HgbA1c, UA, uACR, and uPCR to be performed by a local commercial laboratory in cases where the patient is unable to travel to the study site or the study site is unable to receive or process the samples for delivery to the central laboratory.

²² During the Initial Treatment Period between T2 and T11, collection of the following laboratory samples occurs only at T4 and T8: blood for CMP, CBC + diff., spot urine for uPCR, uACR, and UA.

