The restricted maximum likelihood (REML) method in SAS PROC MIXED will be used to fit the model. The treatment difference in the rate of change in eGFR over 2 years will be estimated from the model along with its standard error, 2-sided confidence interval and p-value. The applicable alpha level will be 5% in a 2-sided test. Denoting time as **T**, the SAS code will be of the form;

```
PROC MIXED DATA=Y COVTEST CL;
  CLASS PATIENT RANDTRT STRAT1 STRAT2;
  MODEL Y = T RANDTRT RANDTRT*T STRAT1 STRAT2 STRAT1*STRAT2/ SOLUTION COVB;
  RANDOM INT T / TYPE=UN PATIENT SOLUTION G GCORR;

  ESTIMATE "INTERCEPT NAR"      INTERCEPT 1 RANDTRT 0 1           / CL ALPHA=0.05;
  ESTIMATE "INTERCEPT PCB"      INTERCEPT 1 RANDTRT 1 0           / CL ALPHA=0.05;
  ESTIMATE "INTERCEPT NAR v PCB" RANDTRT 1 -1 T 0 RANDTRT*T 0 / CL ALPHA=0.05;

  ESTIMATE "SLOPE NAR"          T 1 RANDTRT*T 0 1 / CL ALPHA=0.05;
  ESTIMATE "SLOPE PCB"          T 1 RANDTRT*T 1 0 / CL ALPHA=0.05;
  ESTIMATE "SLOPE NAR v PCB"    T 0 RANDTRT*T 1 -1 / CL ALPHA=0.05;

  ODS OUTPUT "ESTIMATES"=EST;
  ODS OUTPUT SOLUTIONF=F;
  TITLE "RANDOM CO-EFFICIENTS ANALYSIS TOTAL SLOPE EGFR";
RUN;
TITLE;
```

Sensitivity analyses for both key secondary efficacy eGFR endpoints will include:

- Jump to Placebo Multiple Imputation
- Tipping Point Multiple Imputation

- COVID-19

with these analyses executed in the same fashion as described for the primary UPE endpoint.

While prior FDA co-authored publications and supportive simulations demonstrate that the use of fixed weights as per [Cui, Hung and Wang \(1999\)](#) are necessary to avoid alpha inflation associated with the SSRE procedure, an exploratory analysis of eGFR will be performed using an unweighted test statistic for the rate of change in eGFR over 2 years in the high-risk proteinuria group as requested by FDA.

Given the limited eGFR data points during the first 12 weeks of the study, the presence of an early, acute effect on eGFR cannot be meaningfully assessed. Nevertheless, mean change eGFR data will be presented by treatment groups at all sampling timepoints during the 2-year follow-up study period.

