### APPENDIX 3. COMPUTING FISHERS INFORMATION FOR EGFR AT THE TIME OF THE UPE PRIMARY ENDPOINT ANALYSIS

```

options linesize=160 pagesize = 60 dquote nodate nonumber;

libname mdata 'C:\mydata';

/*
filename myfile 'C:\mydata\mydata.log';
proc printto log myfile;
run;
*/

proc printto log=log;
run;

/*
With the primary endpoint analysis to take place with N = 180 high risk proteinuria patients, taking into account the minimum follow-up of 9 months and that recruitment of these 180 patients took 45 months, relative to the planned final analysis of eGFR in the high-risk proteinuria group with N = 280 patients,
*/
%macro datx(nsim,n,acc,k,fup,xfup,vis,ve,vb,d);

*****;
** nsim = number of simulations **;
** k = non uniform accrual parameter k=1 = uniform **;
** k>1 = non uniform **;
** acc = length of accrual months **;
** fup = length follow-up months **;
** xfup = max length of follow-up after last subj **;
** randomised **;
** vis = interval between visits in months **;
** ve = residual squared error after regression **;
** vb = between patient variance component for slope **;
*****;

data y;
nsim=≁
k=&k;
acc=&acc;
fup=&fup;
xfup=&xfup;
vis=&vis;
ve=&ve;
vb=&vb;
if mod(&n,2) = 0 then n=&n;
if mod(&n,2) ne 0 then n=&n+1;
do sim=1 to nsim by 1;
do i=1 to n;
reci=acc*(rand('UNIFORM',0,1)**(1/k));
fupi=(acc-reci)+fup;
if fupi > xfup then fupi=xfup;
v=int(fupi/vis);
vv=vis*v;
do tm=vis to vv by vis;
output;
end;
end;
end;
run;

/*
proc print data =y;
title 'y';
run;

```

```

title;
*/

data y;
  set y;
  g=1;
  if i<=n/2 then g=0;
run;

proc sort data = y;
by sim g i;
run;

proc univariate data = y noprint;
by sim g i;
var tm v;
output out = out2 mean= x v std=sdx n=nvist;
run;

data out2;
  set out2;
  sxxi = (nvist-1)*sdx**2;
  ve=&ve;
  vb=&vb;
  q=(ve/sxxi + vb);
  qinv=(ve/sxxi + vb)**-1;
run;

/*
proc print data = out2;
title 'out2';
run;
title;
*/

proc univariate data = out2 noprint;
by sim g;
var qinv;
output out = out3 sum =sum_qinv ;
run;

/*
proc print data = out3;
title 'out3';
run;
title;
*/

data out3;
  set out3;
  vslope =1/sum_qinv;
  sslope =sqrt(vslope);
run;

proc sort data = out3;
by g;
run;

proc univariate data = out3 noprint;
BY G;
var vslope sslope;
output out = out4 mean=vslope sslope std=sd_vslope sd_sslope n=nsims ;
run;

/*
proc print data = out4;
title 'out4';
run;
title;
*/

```

```

data d&d;
  set out4;
  dat="d&d ";
  nsim=≁
k=&k;
acc=&acc;
fup=&fup;
xfup=&xfup;
vis=&vis;
ve=&ve;
vb=&vb;
n=&n;
run;

%mend;

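### The key secondary eGFR measure is called a total slope from baseline, but as listed its values start at Week 12, so the test is of a slope from Week 12 onward

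*SAP*

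**What the plan says.** Protocol 7.2.2 words the first key secondary endpoint as "The rate of change in eGFR up to 96 weeks from baseline in patients with high baseline proteinuria"; the second is the same measure in all patients. SAP Table 1 gives the population-level summary in both eGFR rows as "the difference between narsoplimab and placebo in eGFR total slope over 96 weeks". The patient-level outcome in those rows is "eGFR values collected at 12, 24, 36, 48, 60, 72, 84 and 96 weeks post randomization". No baseline value is listed, whereas the UPE row of the same table is expressed as a change from baseline.

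The other places that specify an eGFR series start at the same point:
- SAP 1.3.2, registry data: "their eGFR values over 3 to 24 months were assigned to 3 monthly windows to reflect the intended sampling schedule".
- SAP 1.3.2, sample size: "With eGFR measured 3 monthly over 24 months, then" Sxx is set to 378, and SAP 2.9.7 reuses that value.
- SAP Appendix 3 generates visit times with "do tm=vis to vv by vis", so the first visit is at 3 months.
- SAP Appendix 1 keeps baseline eGFR as a separate variable (BASE) and lists the outcome series as W12 to W96.

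The model in SAP 2.9.2.3 has an arm-specific intercept, an arm-specific slope, and time as the actual day relative to randomization. It has no baseline eGFR covariate and does not say which assessment is the first response. The section adds: "Given the limited eGFR data points during the first 12 weeks of the study, the presence of an early, acute effect on eGFR cannot be" judged with any confidence. It promises mean changes by arm at every sampling time.

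The protocol does collect early eGFR. The metabolic panel, which includes eGFR (Protocol Table 2), is drawn at the final Run-In visit and at T12. Between T2 and T11, "collection of the following laboratory samples occurs only at T4 and T8: blood for CMP, CBC + diff" and spot-urine tests (Protocol 20.2.1, footnote 22). SAP Table 2 puts Days 5 to 120 into a single window with target Day 78 and keeps only the closest value.

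**The concern.** A slope fitted to Weeks 12 to 96, with each arm free to have its own intercept, uses only what happens after Week 12. Any separation of the arms between baseline and Week 12, which spans the whole initial dosing course, moves the intercept contrast and leaves the tested slope contrast unchanged. That is a slope from Week 12, not a slope from baseline.

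This is an alpha-controlled endpoint, and SAP 1.3.1 interprets it through a published relation between proteinuria effects and two-year total slope. An early fall on drug would be left out of the confirmatory result, and so would an early gain. Because 2.9.2.3 is silent on baseline, two programmers could also follow the SAP faithfully and produce different confirmatory estimates.

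**Working it through.** **Inputs.** SAP 1.3.2 and Appendix 3, baseline UPE ≥ 2 g/day: residual variance 42.3499 (6.5077²), between-slope variance 0.5411 per month² (0.7356²), difference 3.48 mL/min/1.73 m² per year (0.29 per month), N = 280, two-sided 5%, 85% power. As in the SAP, 12 weeks count as 3 months. Data are taken as complete.

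**Does the plan's Sxx contain a time-zero point?** For 3, 6, …, 24 months the mean is 13.5, and Sxx = 2(1.5² + 4.5² + 7.5² + 10.5²) = 378, the stated value. With time zero added the mean is 12, and Sxx = 2(3² + 6² + 9² + 12²) = 540. The stated figure therefore has no baseline.

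**Reproducing the plan.** N = 4(z_α + z_β)² / δ² × (σ_e²/Sxx + σ_b²)
= 4(1.960 + 1.036)² / 0.29² × (42.3499/378 + 0.5411)
= 278.9 (stated 280).
Power at 280 is 85.1%. The smallest significant difference is 2.27 (stated 2.3). Final information is 280 / (4 × 0.65314) = 107.175 (stated 107.175). The all-patients case gives 449.1 (stated 450).

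**Effect of an early difference.** Let the arms differ by 1 mL/min from Week 12 onward and by nothing at baseline. With balanced data the model's slope contrast weights each time by (t − t̄)/Sxx, so the annual shift is 12 × Σ(t − t̄)h(t)/Sxx, where h = 0 at baseline and 1 from Week 12.
- Table 1 times as listed: h is constant, the deviations sum to zero, and the shift is 0.
- Table 1 times plus baseline: 12 × 12/540 = 0.27 mL/min/year.
- Routinely scheduled panels plus baseline (Weeks 0, 12, 36, 48, 72, 96, that is months 0, 3, 9, 12, 18, 24; mean 11, Sxx = 408): 12 × 11/408 = 0.32 mL/min/year.

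The third line is needed because Table 1 also lists Weeks 24, 60 and 84, where the protocol schedules no routine panel. That is a separate matter.

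| Times (months) | Sxx | Annual shift per 1 mL/min | N for 85% | Power at 280 |
|---|---|---|---|---|
| 3, 6, …, 24 (as listed) | 378 | 0 | 279 | 85.1% |
| 0, 3, …, 24 | 540 | 0.27 | 265 | 86.9% |
| 3, 9, 12, 18, 24 (scheduled) | 262.8 | 0 | 300 | 82.5% |
| 0, 3, 9, 12, 18, 24 | 408 | 0.32 | 276 | 85.6% |

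In calendar weeks the two non-zero shifts are 0.29 and 0.35. In all patients at N = 450, power on the SAP's times goes from 85.1% to 86.9%.

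**Scale.** The documents give no early effect. As an assumption, 1 to 3 mL/min gives 0.27 to 0.80 mL/min/year on the SAP's times plus baseline, which is 8% to 23% of 3.48.

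**Weeks 4 and 8 in the slope model.** Adding these with baseline raises the weight of a Week 12 step to 0.45 on the SAP's times and 0.51 on the scheduled panels. If the difference builds up linearly over the 12 weeks, the weights are 0.31 and 0.35.

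**The case against.** Exclusion of baseline is inferred. SAP 2.9.2.3, the operative model section, never says so. Time relative to randomization and the absence of a baseline covariate are both compatible with baseline as a response. The Table 1 list could be read as the follow-up draws only, and the phrase about 96 weeks from baseline could describe the time horizon. Sxx and Appendix 3 are sizing text, and Appendix 1 concerns imputation. This stands in part: the SAP is ambiguous, not explicit. But every place that does list a series starts it at Week 12 or month 3, and nothing says otherwise.

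An early difference would also be visible. The SAP code outputs the intercept contrast with confidence limits, mean changes by arm are promised, and the limitation is disclosed. This stands too, and it rules out the inference that an early effect would be hidden. It does not bring that effect into the tested result.

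A reader might also infer that eGFR goes unmeasured during the initial course. The documents contradict this: it is drawn at the final Run-In visit and at Weeks 4, 8 and 12. The Week 4 and 8 values drop out only through the Table 2 window, when a value closer to Day 78 exists. With just those two draws strictly inside the period, the SAP's description of early data as limited is fair.

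Finally, the documents do not define total slope, and the cited meta-analysis cannot be consulted here. Whether its slope includes baseline is therefore left open.

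**Conclusion.** The label and the listed data do not match, and the model section does not settle the matter. Fitted as listed, the confirmatory eGFR test is of a slope from Week 12 onward. Per 1 mL/min of early difference that persists, the tested slope moves by 0, against about 0.27 mL/min/year (SAP times plus baseline) or 0.32 (scheduled panels plus baseline) if baseline were a response. These figures assume balanced complete data, a difference complete by Week 12, free arm intercepts as in the SAP's model, and 12 weeks counted as 3 months.

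It would be tempting to conclude that the result is biased in the drug's favour. The documents do not support that: they report no early eGFR effect, and its direction is unknown. Nor is there a type I error or power problem on the plan's own terms, since the stated sample sizes reproduce.

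**What to change.** In both eGFR rows of SAP Table 1 and in 2.9.2.3, state that the final Run-In eGFR enters as the time-zero response. Say whether its time is set to zero or to the actual pre-randomization day. Report the slope from Week 12 onward as a supportive analysis. If baseline is left out on purpose, rename the measure as a slope from Week 12 and say so wherever it is called total slope.

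Align the dependent text: Sxx in 1.3.2 and 2.9.7 (540 on the SAP's times), the Appendix 3 loop and the information fraction, and the outcome series in Appendix 1. Final information becomes 280 / (4 × 0.61953) = 112.99. The interim value of 52.591 has to be re-simulated.

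Add Week 4 and Week 8 windows so that the promised mean-change summary by arm includes those values. Putting them into the slope model is optional and debatable, because a single straight line would then give an early step more weight.

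The cost is SAP text and code; no new data are needed. Power does not suffer at an unchanged slope difference and the same variance components, although those came from registry values that start at 3 months. The real downside is that the total slope becomes less favourable if eGFR falls early on drug. The choice should therefore be settled before the interim snapshot, when the study is unblinded at study level.
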